Appendix 9: Children's Dermatology Life Quality Index

CHILDREN'S DERMATOLOGY LIFE QUALITY INDEX

Hospital No	Diagnosis:	CDLQI SCORE:	
Name:			
Age:			
Address:	Date:		

The aim of this questionnaire is to measure how much your skin problem has affected you OVER THE LAST WEEK. Please tick one box for each question.

1. Over the last week, how itchy, "scratchy", sore or painful has your skin been?	Very much Quite a lot Only a little Not at all	   	
2. Over the last week, how embarrassed or self conscious, upset or sad have you been because of your skin?	Very much Quite a lot Only a little Not at all	   	
3. Over the last week, how much has your skin affected your friendships?	Very much Quite a lot Only a little Not at all	   	
4. Over the last week, how much have you changed or worn different or special clothes/shoes because of your skin?	Very much Quite a lot Only a little Not at all	   	
5. Over the last week, how much has your skin trouble affected going out, playing, or doing hobbies?	Very much Quite a lot Only a little Not at all	   	
6. Over the last week, how much have you avoided swimming or other sports because of your skin trouble?	Very much Quite a lot Only a little Not at all	   	
7. Last week, was it school time? 	If school time: Over the last week, how much did your skin problem affect your school work?	Prevented school Very much Quite a lot Only a little Not at all	   
OR			
was it holiday time? 	If holiday time: How much over the last week, has your skin problem interfered with your enjoyment of the holiday?	Very much Quite a lot Only a little Not at all	   
8. Over the last week, how much trouble have you had because of your skin with other people calling you names, teasing, bullying, asking questions or avoiding you?	Very much Quite a lot Only a little Not at all	   	
9. Over the last week, how much has your sleep been affected by your skin problem?	Very much Quite a lot Only a little Not at all	   	
10. Over the last week, how much of a problem has the treatment for your skin been?	Very much Quite a lot Only a little Not at all	   	

Please check that you have answered EVERY question. Thank you.

©M.S. Lewis-Jones, A.Y. Finlay, May 1993, This must not be copied without the permission of the authors.

Appendix 10: Ichthyosis Quality of Life (IQoL-32)

The following questions concern different periods of time. There are no right or wrong answers. Answer each one as spontaneously as possible by ticking the proposed answer that seems closest to your opinion. If a question does not concern you, tick the corresponding box.

In the past 4 weeks,

1 ... has your skin been red?	 a tremendously	 a lot	 a little	 a not at all	 a not applicable
2 ... has your skin been sensitive or painful (tense, uncomfortable)?	 a tremendously	 a lot	 a little	 a not at all	 a not applicable
3 ... have you had dry or thick skin, with a lot of scales (dead skin)?	 a tremendously	 a lot	 a little	 a not at all	 a not applicable
4 ... has your skin been itchy?	 a tremendously	 a lot	 a little	 a not at all	 a not applicable
5 ... has your skin hurt because of cracking?	 a tremendously	 a lot	 a little	 a not at all	 a not applicable
6 ... because of your ichthyosis, have your eyes bothered you (dryness, pain, watering, impaired vision, redness)?	 a tremendously	 a lot	 a little	 a not at all	 a not applicable
7 ... because of your ichthyosis, have your ears bothered you (earwax plug, impaired hearing, pain, itching)?	 a tremendously	 a lot	 a little	 a not at all	 a not applicable
8 ... did your skin have trouble adapting to temperature and/or weather changes?	 a tremendously	 a lot	 a little	 a not at all	 a not applicable
9 ... have you been bothered by the smell of your skin?	 a tremendously	 a lot	 a little	 a not at all	 a not applicable
10 ... have you felt like your skin was unsightly because of your disease?	 a tremendously	 a lot	 a little	 a not at all	 a not applicable
11 ... does the disease make you feel dirty?	 a tremendously	 a lot	 a little	 a not at all	 a not applicable
12 ... have you felt uncomfortable performing certain everyday actions (such as writing, moving) because of the pains or stiffness caused by ichthyosis?	 a tremendously	 a lot	 a little	 a not at all	 a not applicable
13 ... have you felt "fatigue" in connection with your ichthyosis?	 a tremendously	 a lot	 a little	 a not at all	 a not applicable
14 ... has your scalp bothered you (combing, hair care, pain, or itching)?	 a tremendously	 a lot	 a little	 a not at all	 a not applicable
... have you performed all desired activities (sports and leisure) without fear that others might see your skin?	 a tremendously	 a lot	 a little	 a not at all	 a not applicable
15 ... have you changed your vacation plans or the places you go because the planning required by your ichthyosis was too complicated?	 a tremendously	 a lot	 a little	 a not at all	 a not applicable
16 ... have you felt that your ichthyosis was a handicap (aesthetic or physical), even if you do not consider yourself a handicapped person?	 a tremendously	 a lot	 a little	 a not at all	 a not applicable
17 ... have you experienced mood swings because of ichthyosis?	 a tremendously	 a lot	 a little	 a not at all	 a not applicable
18 ... have you felt sad, discouraged or powerless in the face of your disease?	 a tremendously	 a lot	 a little	 a not at all	 a not applicable
19 ... have you felt lonely or withdrawn because of the disease?	 a tremendously	 a lot	 a little	 a not at all	 a not applicable
20 ... have you experienced a feeling of anger, being "fed up", a sense of injustice because of your disease?	 a tremendously	 a lot	 a little	 a not at all	 a not applicable
21 ... have you felt afraid of the future (treatments losing their effectiveness, worsening, difficulty applying the creams with age)?	 a tremendously	 a lot	 a little	 a not at all	 a not applicable
22 ... have you felt afraid that the disease could restrain a romantic/sexual relationship?	 a tremendously	 a lot	 a little	 a not at all	 a not applicable
23 ... have you had the unpleasant feeling of being stared at or avoided by others?	 a tremendously	 a lot	 a little	 a not at all	 a not applicable
24 ... have you been afraid of being rejected or humiliated by others?	 a tremendously	 a lot	 a little	 a not at all	 a not applicable
25 ... have you felt afraid that others find your skin oily, sticky or rough?	 a tremendously	 a lot	 a little	 a not at all	 a not applicable
26 ... have you had bothersome side effects because of the medications?	 a tremendously	 a lot	 a little	 a not at all	 a not applicable
27 ... has the disease hampered you in performing your work or going about your studies?	 a tremendously	 a lot	 a little	 a not at all	 a not applicable
28 ... has your ichthyosis influenced the way you dress?	 a tremendously	 a lot	 a little	 a not at all	 a not applicable
29 ... have you had a surplus of household chores because of your ichthyosis (skin flakes, oily clothes)?	 a tremendously	 a lot	 a little	 a not at all	 a not applicable
30 ... have you found caring for your skin difficult and unpleasant?	 a tremendously	 a lot	 a little	 a not at all	 a not applicable
31 ... has the care taken too much of your time each day?	 a tremendously	 a lot	 a little	 a not at all	 a not applicable
32 ... has the ichthyosis caused you significant expenses or inconvenient administrative procedures?	 a tremendously	 a lot	 a little	 a not at all	 a not applicable

Appendix 11: Patch Testing

Contact dermatitis represents two forms of exogenous eczematous dermatitis; irritant and allergic contact dermatitis. Irritant dermatitis represents a direct toxic effect of chemicals on epidermal cells resulting in destruction of skin cells and impairment of barrier function. Allergic contact dermatitis is delayed type hypersensitivity (allergy) to small molecular weight molecules and requires initial sensitization and then subsequent elicitation. Allergic contact dermatitis most often occurs within days to weeks after repeated exposure to provocative chemicals. Allergic contact dermatitis to active ingredients and excipients of topical products is well described in the literature.

Patients suspected of having an adverse event of hypersensitivity/allergic contact dermatitis to the topically applied investigational product will be evaluated by the investigator by patch testing. If temporary withdrawal of the investigational medication does not result in amelioration of symptoms, topical corticosteroids may be employed and the patient can discontinue the trial. The presumption of possible allergic contact dermatitis will be based on the investigator's evaluation of an eczematous appearing eruption (erythematous, scaly, vesicular, or eroded patch or plaque) occurring at a previously clear site that is the recent or current recipient of the investigational product.

Patch test application sites should ideally be clinically inactive without any eczematous dermatitis, and as inactive an area of ichthyosis as is clinically practicable. The site of the patch test should not be adjacent to the currently suspected eczematous area. Patients utilizing topical corticosteroids for other local skin reactions should washout for 1 week prior to the initiation of patch testing. Flat areas such as the upper back are preferred, but alternative sites such as the ventral forearm or thigh can be used if the back is not clear. Hair bearing areas should be prepped with a safety razor to ensure adhesion of the test material.

Patch test consents and disposition of signs and symptoms will be recorded in the source document and eCRF. The investigator will apply an approximately 5 mm ribbon of investigational topical medication from the patient's existing medication supply to the interior portion of an IQ ultra patch test chamber (Chemotechnique, Sweden) and secured with additional paper tape. Two additional tests will consist of a vehicle control and white petrolatum that will be supplied by the sponsor upon request. The chambers will remain in place for approximately 48 hours (2 days). Patients will present to the clinical site for removal of the patch test and initial interpretation by the investigator. (See interpretation guideline below from the International Contact Dermatitis Research Group). Patients will return 1-4 days after removal for an additional and final interpretation of the patch test. Patch test results will be recorded in the source document and eCRF.

Patch test interpretation according to the International Contact Dermatitis Research Group (ICDRG)

- ?+ Doubtful
- + Mild reaction, possible erythema, infiltration and papules
- ++ Strong reaction, erythema, infiltration, papules and vesicles
- +++ Very strong reaction, intense erythema, infiltration and coalescing vesicles
- IR** Irritant reaction, of various types

Appendix 12: Abbreviations

AE	Adverse event
ANCOVA	Analysis of covariance
ARCI	Autosomal recessive congenital ichthyosis
β-hCG	Beta-human chorionic gonadotropin
BID	Twice daily
BSA	Body surface area
CDLQI	Children Dermatology Life Quality Index
CFR	Code of Federal Regulations
CI	Congenital ichthyosis
CIOMS	Council for International Organizations of Medical Sciences
CMH	Cochran-Mantel-Haenszel
CONSORT	Consolidated Standards of Reporting Trials
COVID-19	Coronavirus Disease 2019
CRO	Clinical research organization
DLQI	Dermatology Life Quality Index
DNA	Deoxyribonucleic Acid
eCRF	Electronic case report form
eDiary	Electronic diary
EOS	End of study
ePRO	Electronic patient-reported outcome
FDA	Food and Drug Administration
FSH	Follicle stimulating hormone
GCP	Good Clinical Practice
GMP	Good Manufacturing Practice
HIPAA	Health Insurance Portability and Accountability Act
HRT	Hormonal replacement therapy
ICF	Informed consent form
ICH	International Council for Harmonisation
IEC	Independent Ethics Committee
IGA	Investigator Global Assessment
I-NRS	Itch-Numeric Rating Scale
IQoL-32	Ichthyosis Quality of Life -32
IRB	Institutional Review Board

ITT	Intent-to-treat
IWRS	Interactive Web Response System
LI	Lamellar ichthyosis
LSR	Local skin reactions
MAR	Missing at random
MCMC	Markov Chain Monte Carlo
MedDRA	Medical Dictionary for Regulatory Activities
MI	Multiple imputation
mITT	Modified intent-to-treat
OTC	Over-the-counter
PP	Per-protocol
PT	Preferred term
QD	Once a day
QoL	Quality of Life
RA	Retinoic acid
ROAT	Repeat open application test
RXLI	Recessive X-linked ichthyosis
SAE	Serious adverse event
SAP	Statistical analysis plan
SD	Standard deviation
SoA	Schedule of Assessments
SOC	System organ class
STS	Steroid sulfatase
SUSAR	Suspected unexpected serious adverse reactions
TEAE	Treatment-emergent adverse event
TGM1	Transglutaminase type 1
ULN	Upper limit of normal
UPT	Urine pregnancy test
US	United States
UV	Ultraviolet
VIIS	Visual Index for Ichthyosis Severity
VIIS-50	Visual Index for Ichthyosis Severity – Scale “treatment success”
WOCBP	Women of childbearing potential

1.0 Introduction

This is an addendum to the TMB01-301 SAP Version 3.0 dated 27 February 2024. The addendum specifies additional analyses, clarifies calculation of the percent reduction in VIIS score, and specifies handling of a potential convergence issue in the multiple imputations. Unless otherwise stated, the SAP Version 3.0 still applies.

2.0 Worst Itch-QoL (WI-NRS) 4-point improvement – additional analyses

Due to an unexpectedly low number of subjects with a baseline WI-NRS score ≥ 7 , additional analyses will be made using the threshold of a baseline WI-NRS score ≥ 4 , ie. including in the analysis as many subjects as possible who have the possibility of obtaining a 4-point reduction. Except for the baseline threshold, the analyses will be performed as specified in the SAP Version 3.0, Section 5.2.2.3 (Week 12 analysis) and Section 5.4.3 (Week 24 analysis).

3.0 DLQI/CDLQI 4-point improvement – additional analyses

Due to an unexpectedly low number of subjects with a baseline DLQI score ≥ 11 (adults) or baseline CDLQI score ≥ 13 (pediatric subjects), additional analyses will be made using the threshold of a baseline DLQI or CDLQI score ≥ 4 , ie. including in the analysis as many subjects as possible who have the possibility of obtaining a 4-point reduction. Except for the baseline threshold, the analyses will be performed as specified in the SAP Version 3.0, Section 5.4.2.

4.0 IGA score (combined scaling and fissuring) at Week 24 – additional analyses

In addition to the proportion of subjects with a ≥ 2 grade IGA improvement at Week 24, the proportion of subjects with a 1 grade improvement at Week 24 and the proportion of subjects with an IGA score of 0 or 1 at Week 24 will be tabulated. This will be done for all subjects randomized to maintenance treatment, as well as in the subgroup of subjects initially randomized to TMB-001 0.05% with a ≥ 2 grade IGA improvement at Week 12, the subgroup of subjects initially randomized to

TMB-001 0.05% with a 1 grade IGA improvement at Week 12 and in the subgroup of subjects initially randomized to TMB-001 0.05% with an IGA score of 0 or 1 at Week 12. The same estimand and multiple imputation approach as specified in the SAP Version 3.0, Section 5.3, for the ≥ 2 grade IGA improvement at Week 24 endpoint will be used. In addition, observed cases analyses will be provided. For subjects initially randomized to TMB-001 0.05%, results will be presented according to re-randomized treatment (BID or QD) using the open-label dosing presentation.

5.0 VIIS Scaling score – clarification

The percent reduction in VIIS scaling score will be calculated as the percent reduction in the average VIIS scaling score, among all treated areas with a baseline VIIS-scaling score ≥ 3 . The calculation based on the average is equivalent with the definition of the primary endpoint in the Phase 2b trial (235-9051-202). As the ASCEND protocol did not specifically state that all areas with a baseline VIIS-scaling score ≥ 3 were to be treated, only areas that were identified as being treated at baseline will be included in the analyses, regardless of if treatment in those areas were discontinued at subsequent visits.

6.0 Adverse events – addition of exposure adjusted incidence rates

As requested by the FDA, all AE tables will include exposure adjusted incidence rates (EAIRs) per 100 years of exposure in addition to the number and proportion of subjects with AEs. Exposure adjusted incidence rates for a specific type of AE will be calculated as the number of subjects with the specific type of AE, divided by the total person-years at risk for the specific type of AE. For subjects with events, the time at risk is the time from the first IMP application to onset of the first event of the specific type, for subjects with no event of the specific type, the time at risk is the time from the first IMP application to the last visit.

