1.3.1 Overview of Study Design

The study consists of three periods:

- **Period 1 – Induction (3 weeks):**

At the beginning of the 3-week induction period, eligible subjects will be randomized (2:1 ratio) to either TMB-001 0.05% once-a-day (QD) or Vehicle QD treatment, with use of mandatory standardized bland emollient (Cetaphil™) provided by the Sponsor.

- **Period 2 – Treatment (9 weeks):**

The dosing frequency in the 9-week treatment period will be increased in each treatment group to TMB-001 0.05% or Vehicle twice a day (BID). Mandatory bland emollient will be discontinued.

- **Period 3 – Maintenance (12 weeks):**

At Week 12, eligible subjects in the TMB-001 treatment group will be randomized (1:1 ratio) to open-label treatment with TMB-001 0.05% BID or QD. To be eligible, subjects must have achieved a \geq 1-point reduction in IGA score from Baseline.

Subjects with $<$ 1-point reduction in IGA score from Baseline will be discontinued from the study.

Vehicle-treated subjects who achieved $<$ 1-point reduction in IGA score from Baseline are eligible to cross over to the TMB-001 0.05% BID treatment group. Subjects with a \geq 1-point reduction in IGA score from Baseline will be discontinued from the study.

Subjects at the end of the study or subjects discontinued from the study at any time will be followed-up for an additional 2 weeks for the monitoring of adverse events.

Optional Maximal Use Arm

Adult and pediatric subjects, at a subset of preselected centers, will be enrolled in an open-label Optional Maximal Use arm to evaluate the systemic exposure and safety of topical TMB-001 0.05% ointment for the treatment of CI under maximal use conditions. Initially, adult CI subjects (\geq 17 years; n=16) and pediatric subjects (12-16 years; n=7-9) will be dosed for 14 days with TMB-001 0.05% BID. Following an interim PK analysis and based on the exposure data for subjects aged \geq 12 years, pediatric subjects aged 6 to 11 years (n=7-9) will begin dosing with TMB-001 0.05% BID for 14 days. Following the 14-day PK assessment period, subjects will receive TMB-001 0.05% BID treatment for 10 additional weeks to provide additional safety and limited efficacy data.

The schedule of assessments for both the Phase 3 study and the optional maximal use arm can be found in the study protocol.

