1.3.3 Sample Size Justification

Sample size calculations are based on the results of the Phase IIb study "A Randomized, Parallel, Double-Blind, Vehicle-Controlled Study to Evaluate the Safety and Efficacy of Two Concentrations of Topical TMB-001 for the Treatment of Congenital Ichthyosis". Response rate assumptions for the primary endpoint (proportion of subjects with IGA ≥ 2 -point improvement from Baseline) are 50% in the TMB-001 group and 10% in the vehicle group. A total sample size of 110 subjects randomized in a 2:1 ratio between TMB-001 0.05% and Vehicle will have approximately 90% power to detect a difference of 40% between the treatment groups at the 1% significance level (2-sided). The sample size also covers the proportion of approximately 15% of dropouts and non-evaluable subjects.

No formal power calculations were performed for the optional maximal use arm.

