3.11.3 Safety

The primary data presentation for all safety analyses (henceforth referred to as 'primary safety data presentation') will have the following table header:

TMB-001 0.05% (N=xx)	Vehicle (N=xx)	Overall (N=xx)
----------------------------	-------------------	-------------------

The TMB-001 0.05% and Vehicle columns will represent the subjects initially randomized to either TMB-001 0.05% or vehicle, regardless of the second randomization allocation in Period 3.

Additionally, a data presentation specific to Period 3 will be used:

	OL TMB-001 0.05% BID (N=xx)			
OL TMB-001 0.05% QD (N=xx)	TMB-001 0.05% in	Vehicle in Blinded	Total OL TMB- 001 0.05% BID (N=xx)	Overall (N=xx)

	Blinded Phase (N=xx)	Phase (N=xx)		
--	-------------------------	-----------------	--	--

This data presentation (henceforth referred to as 'open-label dosing safety data presentation') will be used for all analyses of safety endpoints specifically during Period 3, comparing TMB-001 0.05% BID and QD maintenance dosing.

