7.2 Adverse Events

All adverse events (AEs) will be coded using the MedDRA v25.0 coding system and displayed in tables and data listings using system organ class (SOC) and preferred term. Missing and partial dates will be handled as described in Section 3.9.2.

Analyses of AEs will be performed for those events that are considered treatment-emergent, where treatment-emergent is defined as any AE with onset after the first application of study drug through 30 days after the last study drug application, or any event that was present at baseline but worsened in intensity or was subsequently considered drug-related through 30 days after the last study drug application.

Adverse events will be summarized by subject incidence rates; therefore, in any tabulation, a subject contributes only once to the count for a given AE in both SOC and preferred term. The table will be sorted by descending frequency, based on the overall column of the data presentation.

Adverse events will be reported separately by event type; reporting of SOCs and preferred term will be as described above.

The number and percentage of subjects with any treatment-emergent adverse event (TEAE), with any TEAE assessed as related to study drug (possibly or probably), with any serious TEAE, any non-serious TEAE, with any serious TEAE potentially related to study drug, any non-serious TEAE potentially related to study drug, with any common (occurring in $\geq 5\%$ of subjects) TEAE, or with any TEAE leading to study drug withdrawal will be provided. Additional tabulations will be provided for TEAEs by maximum severity, and TEAEs by strongest relationship to study drug.

All analyses above will be performed using both data presentations described in Section 3.9.3, where TEAEs will contribute to each summary only if they began in the corresponding period. For example, a TEAE starting during Periods 1 or 2 will be reported using the primary safety data presentation, and a TEAE starting during Period 3 will be reported using the open-label dosing data presentation.

Additionally, the proportion of subjects experiencing a TEAE through Week 12 will be reported along with exact binomial 95% confidence intervals, using the primary safety data presentation. The proportion of subjects experiencing a TEAE through Week 24 will be reported along with exact binomial 95% confidence intervals, using the open-label dosing data presentation.

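### The addendum's exposure-adjusted AE rates divide events from one period by person-time that is not limited to that period

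*SAP*

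**What the plan says.** SAP Addendum section 6.0 adds EAIRs to all AE tables at the FDA's request. The numerator is the number of subjects with the type of event; the denominator is person-years at risk. For subjects with an event, "the time at risk is the time from the first IMP application to onset of the first event of the specific type". For subjects without one, "the time at risk is the time from the first IMP application to the last visit".

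The addendum's introduction says: "Unless otherwise stated, the SAP Version 3.0 still applies". Three parts of SAP Version 3.0 therefore still govern these tables:

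- **Section 7.2** produces the AE analyses in two presentations, one for Periods 1-2 and one for Period 3, and "TEAEs will contribute to each summary only if they began in the corresponding period".
- **Section 3.11.3** places subjects in the TMB-001 and Vehicle columns by initial randomization, "regardless of the second randomization allocation in Period 3".
- **Section 1.3.1** sends TMB-001 subjects into Period 3 only if their IGA score fell by at least 1 point. The vehicle rule is the reverse: those with less than a 1-point fall "are eligible to cross over to the TMB-001 0.05% BID treatment group", and the others leave the study.

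Section 7.1 defines first- and last-dose dates for Periods 1-2, for Period 3 and for all periods combined, but for exposure and compliance only. Addendum section 6.0 does not refer to them.

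**The concern.** The numerator is restricted to a period; the denominator starts at the first dose in the study and can run to the last visit.

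In the Period 1-2 tables, a subject who is event-free at Week 12 and continues adds up to about 12 weeks in which no event can be counted. For a vehicle crossover, that time is spent on TMB-001 but sits in the Vehicle column.

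In the Period 3 tables, the clock includes the 12 weeks before the period began. It is also unclear what counts as the first event there. If it is the first in the study, a subject with an earlier event of that type stops adding time before Period 3 starts, yet can still be counted for a Period 3 event.

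Exposure adjustment is meant to make groups with different follow-up comparable. Here it could create a difference between arms with equal true rates, because the two arms enter Period 3 by opposite rules.

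**Working it through.** The documents state no EAIR, AE incidence or person-time total, so there is no figure to reproduce. The check compares the clock as written with a clock limited to the table's own 12 weeks.

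**Inputs**
- Periods 1-2 together and Period 3 last 12 weeks each (SAP 1.3.1).
- 12-week incidence p: not given; 5-50% assumed.
- Share c continuing into Period 3: not given. SAP 1.3.3 assumes rates of at least 2-point improvement that "are 50% in the TMB-001 group and 10% in the vehicle group", and allows for "approximately 15% of dropouts and non-evaluable subjects". Treating that 15% as lost before Week 12 and letting every eligible subject enter:
  - TMB-001: from 0.85 × 0.50 = 42.5% (everyone with a 2-point gain meets the 1-point rule) up to 85%.
  - Vehicle: at most 0.85 × 0.90 = 76.5%.
  - A lower end of 30% is assumed.
- Constant hazard h with 1 − exp(−12h) = p; continuation independent of AE status. The last visit is first taken as Week 12 or Week 24.

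**Matched person-time per subject:** m = p/h = 11.70, 10.76 and 8.66 weeks at p = 0.05, 0.20 and 0.50.

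**Period 1-2 tables: EAIR as written ÷ matched EAIR**
- Period 3 events do not stop the clock: m / (m + 12(1 − p)c). At p = 0.05, c = 0.85: 11.70/(11.70 + 9.69) = 0.547. At p = 0.50, c = 0.30: 8.66/(8.66 + 1.80) = 0.828.
- Period 3 events stop the clock (same hazard): 1 / (1 + (1 − p)c) = 0.553 and 0.870 at the same points.

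The factor is below 1 whenever c > 0. Taking the two-week safety visit as the last visit lowers it further: over 5-60% incidence and 50-100% continuing, 0.51-0.77 becomes 0.47-0.71.

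**Worked example:** p = 0.20; 74 TMB-001 (SAP 1.3.2) and 110 − 74 = 36 Vehicle; 80% and 50% continuing (assumed); 52.18 weeks per year.

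| | TMB-001 | Vehicle |
|---|---|---|
| Subjects with event | 14.8 | 7.2 |
| Matched person-years | 74 × 10.76/52.18 = 15.25 | 36 × 10.76/52.18 = 7.42 |
| Matched EAIR per 100 PY | 97.0 | 97.0 |
| Added person-years | 74 × 0.8 × 0.8 × 12/52.18 = 10.89 | 36 × 0.8 × 0.5 × 12/52.18 = 3.31 |
| Person-years as written | 26.14 | 10.73 |
| EAIR as written | 56.6 | 67.1 |

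The apparent ratio is 56.6/67.1 = 0.84, although the true rates are equal. If Period 3 events stop the clock, person-years are 25.02 and 10.39, the rates 59.2 and 69.3, and the ratio 0.85.

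**Between arms, p = 0.05, equal true rates:** ratio 0.84 at 80% vs 50% continuing, 1.00 at equal shares, 1.23 at 42.5% vs 76.5%.

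**TMB-001 time in the Vehicle column, 30-76.5% crossing over, p = 0.05-0.20:** 12(1 − p)c / (m + 12(1 − p)c) gives 21-43%. If Period 3 events stop the clock, (1 − p)c / (1 + (1 − p)c) gives 19-42%. Across both readings: 19-43%.

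**Period 3 tables: EAIR as written ÷ matched EAIR**
- First event means first in Period 3: m/(12 + m) = 0.494, 0.473, 0.419 at p = 0.05, 0.20, 0.50.
- First event means first in the study, same hazard throughout: 1/(2 − p) = 0.513, 0.556, 0.667.
- First event means first in the study, share q with an earlier event averaging day 20 (2.86 weeks, assumed), p = 0.20: 10.76 / (2.86q + 22.76(1 − q)) = 0.52 at q = 10%, 0.64 at 30%, 0.84 at 50%, 0.99 at 60%, 1.57 at 80%. Break-even is at about q = 60%.

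**The case against.** The best defence is that a coherent reading exists. Section 6.0 speaks of person-years at risk, section 7.2 makes the summaries period-specific, and section 7.1 already splits exposure by period. A programmer might therefore use period-specific time, leaving only a missing cross-reference. But section 7.1 confines its dates to exposure and compliance, and section 6.0 gives explicit start and stop rules that say otherwise. That intention is not in the text.

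Other points limit the scope or size:

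- **Through Week 24.** Section 7.2 also reports the proportion with a TEAE through Week 24, which one clock from first dose could suit. This stands; the problem lies in the period-specific tables.
- **Treatment received.** Section 2.3 analyses the Safety population by treatment actually received, which sits badly with crossover time in the Vehicle column. Section 3.11.3 nevertheless defines those columns by initial randomization.
- **Between-arm scenarios.** The 42.5% vs 76.5% pair requires that nobody improves by exactly 1 point, and the 80% vs 50% pair has no source in the documents. Both illustrate direction; neither is a forecast.
- **Overstatement in Period 3.** It needs more than half of subjects to have had an earlier event of the same type, outside the 5-50% incidence range used elsewhere. At 50% and day 20 the factor is still below 1 (0.88, 0.84 and 0.74 at p = 0.05, 0.20 and 0.50). Day 20 has no direct AE source: the Phase IIb timing in Protocol 2.2 is for local skin reactions under twice-daily dosing.
- **Topline at Week 12.** That data cut (SAP 3.1) would not repair the final tables.
- **Descriptive only.** This is true and limits the consequence.

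**Conclusion.** The concern holds. As written, the EAIR denominator is not tied to the period whose events are counted.

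For the Period 1-2 tables, understatement is certain whenever event-free subjects continue, under either reading of first event. The size, 0.55-0.87 of the matched rate, rests on the assumed incidence and continuation shares and on a constant hazard. A distortion between arms is possible in either direction and vanishes if equal shares continue; the documents do not give those shares.

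For the Period 3 tables the person-time is wrong. The rate is too low in most scenarios examined, but the rule does not fix the direction, because first event is undefined and a large share with earlier events reverses it.

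The EAIRs are untested descriptive rates. AE counts and proportions, the efficacy tests, alpha and sample size are unaffected. It should still be fixed: the FDA asked for these rates, and they will be read across arms.

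**What to change.** Amend Addendum section 6.0 to define person-time separately for each presentation, using the period dates in SAP 7.1, and state that the first event is the first of its type that began in the table's own period.

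- **Period 1-2 tables:** from first application to the earliest of the first event in Periods 1-2, the first Period 3 application, or, for subjects who do not continue, the end of AE observation.
- **Period 3 tables:** from the first Period 3 application to the first event that began in Period 3, or to the last visit. State that an earlier event of the same type does not stop this clock.
- **Any through-Week-24 rate:** if one is wanted, give it its own stated clock.

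The cost is one paragraph and a programming change; no new data are needed.
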